12.1.3 Methods for Evaluation of Measurable Disease

Hematopathology – The percentage of blasts found on the aspirate differential as read by the hematopathologist at the enrolling institution will be used to evaluate response.

Peripheral Blood CBC and Differential – The ANC, platelet count, and differential, including blast percentage from both automated and manual differentials, will be used. If both an automated and manual differential are performed, the latter will be used to evaluate the peripheral blast percentage.

FDG-PET - While FDG-PET response assessments need additional study, it is sometimes reasonable to incorporate the use of FDG-PET scanning to assess diagnosis and progression (particularly possible 'new' disease). This would only be applicable to patients with extramedullary disease. New lesions on the basis of FDG-PET imaging can be identified according to the following algorithm:

- a. Negative FDG-PET at baseline, with a positive FDG-PET at follow-up is a sign of PD based on a new lesion.
- b. No FDG-PET at baseline and a positive FDG-PET at follow-up: If the positive FDG-PET at follow-up corresponds to a new site of disease, this area should be biopsied to determine if it represents progression of disease. Such cases should be discussed with the medical monitor.
- c. FDG-PET may be used to upgrade a response to a CR for a patient with extramedullary disease, no bone marrow involvement, and no other means by which to evaluate their disease involvement (e.g. physical exam) in a manner similar to a biopsy in cases where a residual radiographic abnormality is thought to represent fibrosis or scarring. However, it must be acknowledged that such an approach may lead to false positive CR due to limitations of FDG-PET and biopsy resolution/sensitivity.

Note: A 'positive' FDG-PET scan lesion means one which is FDG avid with an uptake greater than twice that of the surrounding tissue on the attenuation corrected image.

12.1.4 Response Criteria

12.1.4.1 Evaluation of Response as per 2017 ELN Guidelines¹⁹

Complete Remission (CR): Bone marrow blasts < 5%; no circulating blasts, no blasts with Auer rods, no extramedullary disease; ANC > 1000 per microliter, platelets > 100,000 per microliter

Complete Remission with Incomplete Count Recovery(CRi): Bone marrow blasts < 5%; no circulating blasts, no blasts with Auer rods, no extramedullary disease; ANC ≤ 1000 per microliter and / or platelets ≤ 100,000 per microliter

Morphologic Leukemia-Free State (MLFS): Bone marrow blasts < 5%; no blasts with Auer rods, no extramedullary disease; no hematologic recovery required

Partial Remission (PR): All hematologic criteria of CR; decrease in bone marrow blasts to 5-25%; decrease in pre-treatment bone marrow blasts by at least 50%

Progressive Disease (PD): Evidence for an increase in bone marrow blast percentage and/or increase of absolute blast counts in the blood:

- > 50% increase in marrow blasts over baseline (a minimum 15% point increase is required in cases with < 30% blasts at baseline; or persistent marrow blast percentage of >70% over at least 3 mo; without at least a 100% improvement in ANC to an absolute level ($>0.5 \times 10^9 /L$ [500/ μ L], and/or platelet count to $>50 \times 10^9 /L$ [50,000/ μ L] nontransfused); or
- > 50% increase in peripheral blasts (WBC x % blasts) to $>25 \times 10^9 /L$ ($>25,000/\mu$ L) (in the absence of differentiation syndrome); or
- New extramedullary disease

Stable Disease (SD): Absence of CR, CRi, MLFS, PR; criteria for progressive disease not met

12.1.4.2 Evaluation of Non-Target Lesions

N/A

12.1.4.3 Evaluation of Best Overall Response

The best overall response is the best response recorded from the start of the treatment until disease progression/recurrence (taking as reference for progressive disease the smallest measurements recorded since the treatment started). The patient's best response assignment will depend on the achievement of both measurement and confirmation criteria.

The overall response rate includes achievement of CR, CRi, MLFS, and PR.

12.1.5 Duration of Response

Duration of overall response: The duration of overall response is measured from the time measurement criteria are met for CR or PR (whichever is first recorded) until the first date that recurrent or progressive disease is objectively documented (taking as reference

for progressive disease the smallest measurements recorded since the treatment started).

The duration of overall CR is measured from the time measurement criteria are first met for CR until the first date that progressive disease is objectively documented.

Duration of stable disease: Stable disease is measured from the start of the treatment until the criteria for progression are met, taking as reference the smallest measurements recorded since the treatment started, including the baseline measurements.

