1. OBJECTIVES

1.1 Primary Objectives

1.1.1 Phase Ib Safety / Tolerability Run In - Primary Objective:

- To determine if the combination of pinometostat, at a dose of 54 or 90mg/m²/day, and azacitidine, at a dose of 75 mg/m² daily for 7 days, is safe and tolerable in patients with MLL-rearranged acute myeloid leukemia, either in the relapsed / refractory setting or in those who choose not to undergo standard induction therapy in the previously untreated setting

1.1.2 Phase II Primary Objective:

- To determine the preliminary efficacy, as determined by overall response rate (CR, CRi, PR, and MLFS), of pinometostat administered at the maximum tolerated dose from the phase 1b, combined with azacitidine administered at 75 mg/m² daily for 7 days, in patients with MLL-rearranged acute myeloid leukemia, either in the relapsed / refractory setting or in those who choose not to undergo standard induction therapy in the previously untreated setting. Patients will be treated with 6 cycles of therapy on trial, with the option to continue if they are deriving significant clinical benefit. As only two dose levels are being studied, the MTD may not be reached. In this case, a recommended phase 2 dose (RP2D) of either 54 or 90 mg/m² pinometostat will be evaluated in the Phase 2 portion of the study, based on the dosing used in the previous phase 1 trial of single-agent pinometostat¹.

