- Response to combination therapy defined as CR, CRi, PR, or MLFS, with or without minimal residual disease (MRD), on bone marrow biopsy as defined by the 2017 European Leukemia Network guidelines will be assessed. Baseline bone marrow biopsy will be performed within 14 days prior to starting therapy, at the end of cycle 1 (day 28 +/- 2 days or time of count recovery), at the end of cycle 3 (+/- 2 days or at the time of count recovery after three cycles of azacitidine administration), at the end of cycle 6 (+/- 2 days or at the time of count recovery after six cycles of azacitidine administration), and / or at the time of therapy discontinuation +/- 3 days. Patients who have stable disease after 4 cycles of combination therapy or progressive disease at any time should be taken off the trial.

Phase II Primary Endpoint Analytic Plan:

- Response rate will be defined as the number of patients who achieve a CR, CRi, PR, or morphologic leukemia-free state (MLFS), with or without MRD, at any time point. Patients will be evaluated through the time of count recovery after 6 cycles of combination therapy.
- A Simon two-stage minimax design will be employed whereby a 20% response rate is considered not promising, a 40% response rate is considered promising, and the probabilities of a type I error (falsely accepting a non-promising therapy) and type II error (falsely rejecting a promising therapy) are set at 0.10 and 0.10, respectively. In the first stage of this design, 19 patients will be accrued. All patients will be followed for a minimum of 24 weeks. If at least 4 patients respond then an additional 17 patients will be accrued to the second stage. At the end of the trial, if 11 or more patients respond out of a total of 36 patients, then this combination will be considered worthy of further investigation. This design yields at least a 0.90 probability of a positive result if the true response rate is at least 40% and yields a 0.90 probability of a negative result if the true response rate is 20%.

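### Duration of overall response starts only at CR or PR, although the response rate also counts CRi and MLFS, so some counted responders get no start date or a late one

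*Combined protocol and SAP*

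**What the plan says.** Three places define the response rate or its components, and they agree:

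- Section 1.1.2 (Phase II Primary Objective) sets out to estimate efficacy "as determined by overall response rate (CR, CRi, PR, and MLFS").
- Section 9.1 (Phase II Primary Endpoint Analytic Plan) says: "Response rate will be defined as the number of patients who achieve a CR, CRi, PR, or morphologic leukemia-free state (MLFS"), counted whenever it occurs.
- Section 12.1.4.3 (Evaluation of Best Overall Response) says: "The overall response rate includes achievement of CR, CRi, MLFS, and PR".

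Section 9.4 uses the same four categories for the description by relapsed/refractory or untreated stratum.

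Section 12.1.5 then defines the duration of overall response as measured "from the time measurement criteria are met for CR or PR (whichever is first recorded"), ending at documented recurrence or progression. CRi and MLFS are not named. The same section separately defines a duration of overall CR, which starts at CR. No other section gives a start date for a CRi or MLFS responder.

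**The concern.** The adjective overall covers four categories in Section 12.1.4.3 and two in Section 12.1.5. Followed literally, the duration rule does two things to patients already counted as responders. It leaves out those who never reach CR or PR, and it discards the early part of the response in those who reach CR after CRi or MLFS.

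The first effect selects responders with recovered counts. The second shortens their durations. The two can pull a summary in different directions, so the net bias cannot be signed in advance. Two analysts could also report durations on different denominators. What is at stake is whether a reported duration describes the same patients as the reported response rate.

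Such patients are plausible here. CRi and MLFS are the responses that do not need full count recovery, and Section 7 states that neutropenia and thrombocytopenia are expected on treatment.

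**Working it through.** **1. Are CRi and MLFS really outside CR and PR?** Section 12.1.4.1 gives the criteria.

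| Category | Marrow blasts | Counts |
|---|---|---|
| CR | < 5% | "ANC > 1000 per microliter, platelets > 100,000 per microliter" |
| CRi | < 5% | "ANC ≤ 1000 per microliter and / or platelets ≤ 100,000 per microliter" |
| MLFS | < 5% | no recovery needed |
| PR | 5-25%, with a fall of at least 50% | as for CR |

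The full MLFS entry reads: "Bone marrow blasts < 5%; no blasts with Auer rods, no extramedullary disease; no hematologic recovery required".

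- CRi and CR: the count criteria are complementary, so a patient cannot meet both at one assessment.
- CRi or MLFS and PR: blasts below 5% and blasts of 5-25% cannot both hold.
- MLFS and CR: a patient whose best response is MLFS has, by that classification, not met CR.

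A best response of CRi or MLFS therefore never triggers a clock that starts at CR or PR.

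**2. How late can the clock start?** Section 12.1 schedules response assessment at the end of cycles 1, 3 and 6. Section 6.1 gives a 28-day cycle.

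- End of cycle 1: 1 × 28 = day 28 (week 4)
- End of cycle 3: 3 × 28 = day 84 (week 12)
- End of cycle 6: 6 × 28 = day 168 (week 24)

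Delay = day of first CR minus day of first CRi or MLFS:

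- cycle 1 to cycle 3: 84 - 28 = 56 days = 8 weeks
- cycle 3 to cycle 6: 168 - 84 = 84 days = 12 weeks
- cycle 1 to cycle 6: 168 - 28 = 140 days = 20 weeks

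**3. How many responders could have no start date?** Section 9.1 calls the combination worthy of further study at 11 or more responders of 36, so 11 is the smallest successful count. The share with only CRi or MLFS is not in the documents. Assume a share s, and that none of these patients later reach CR or PR:

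- s = 10%: 11 × 0.10 = 1.1, about 1
- s = 25%: 11 × 0.25 = 2.75, about 3
- s = 50%: 11 × 0.50 = 5.5, 5 or 6

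**4. Does the design depend on this?** The documents state no figure for duration, so the only figures to reproduce are those of the Simon design in Section 9.1: 19 + 17 = 36 patients, continue at 4 or more responses, success at 11 or more. With response probability p,

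P(success) = Σ (x = 4 to 19) P[Bin(19, p) = x] × P[Bin(17, p) ≥ 11 - x].

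At p = 0.20 this gives 0.0861 (limit 0.10). At p = 0.40 it gives 0.9024 (target 0.90). An exhaustive minimax search returns the same design. Response enters as a count and duration does not enter at all, so no design figure changes.

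**The case against.** **Duration is not a planned endpoint.** It is absent from the objectives in Section 1 and from every endpoint and analytic plan in Section 9; it is only defined in Section 12. This stands and limits the weight of the point. A reader might infer that the primary result is compromised, or that the response rate and a planned duration result cannot be read together. The documents support neither: the primary endpoint does not use duration, and Section 9 plans no duration result. Section 9.4 does promise Kaplan-Meier estimates by stratum, but it names no time-to-event variable. Progression-free survival, defined in Section 12.1.6, is at least as likely a candidate.

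**The four-category definition is not universal.** A reader might infer that every other section uses it. Section 9.5.2 lists complete response, partial response and MLFS but no separate CRi, and a continuation rule in Section 7 refers to CR or PR. If complete response in Section 9.5.2 includes CRi, a CRi would start the clock and that part of the point falls away. Section 12.1.4.1 defines CRi separately, so this reading is not secure. A best response of MLFS stays outside on either reading, because Section 9.5.2 itself lists MLFS apart from complete and partial response. The folded reading would shrink the gap, however: as worded, the CR and CRi count criteria together cover all counts, so only circulating blasts separate MLFS from both.

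**The sizes are soft.** This also stands. The delays are nominal gaps between scheduled marrows. Section 9.1 allows a marrow to wait for count recovery, which may reduce CRi and MLFS calls. Blood counts taken between marrows could date a CR earlier, and the documents do not say whether CR must be dated at a marrow. The 20-week case also needs the cycle 3 assessment not to show CR or PR. A reader might settle on a narrower range, such as 3 to 6 patients, but nothing in the documents supports its lower bound.

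**The restriction may be deliberate.** Nothing says so or gives a reason, and the separate duration of overall CR already supplies a narrower measure.

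**Conclusion.** The mismatch is real. Every section that defines the response rate or primary endpoint counts CR, CRi, PR and MLFS, while Section 12.1.5 starts the duration of overall response at CR or PR alone. Best responses of MLFS have no duration on any reading; best responses of CRi have none on the definitions in Section 12.1.4.1. Later conversion to CR costs nominally 8, 12 or 20 weeks.

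The number without a duration is about 1 to 6 of 11 responders. That range rests on an assumed 10-50% share with only CRi or MLFS and on none of them later reaching CR or PR. Neither assumption comes from the documents.

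This is a definitional fault in a descriptive measure. It is worth correcting before any duration is reported, but it does not touch the primary result, the sample size or the decision rules.

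**What to change.** In Section 12.1.5, start the duration of overall response at the first date on which criteria are met for CR, CRi, MLFS or PR. Any duration reported then covers the same responders as the response rate. Keep duration of overall CR unchanged as the narrower measure. If restriction to CR and PR is in fact intended, say so and report how many counted responders it leaves out.

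The cost is one sentence. Marrow results and blood counts are already collected under the Study Calendar (Section 11), so no new data are needed. Section 13.1 already requires a protocol amendment before phase 2 enrolment, and the change can go there.

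Two limits remain. Making duration a planned analysis would need a further entry in Section 9. And follow-up ends 1 month after removal from study (Section 6.6), so durations may be cut short for patients who leave while in response, whichever start date is used.

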12.1.6 Progression-Free Survival

Progression-free survival (PFS) will be assessed, defined as the duration of time from start of treatment to time of progression or death, whichever occurs first.

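### CR duration and PFS do not count relapse as an event unless it also meets the progression criteria, and Section 12 gives conflicting reference points for progression

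*Combined protocol and SAP*

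**What the plan says.** Five parts of Section 12 bear on this.

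- **Progressive disease (12.1.4.1).** The first marrow criterion is "> 50% increase in marrow blasts over baseline (a minimum 15% point increase is required in cases with < 30% blasts at baseline"). Three other routes exist: "persistent marrow blast percentage of >70% over at least 3 mo" without a stated improvement in counts; a "> 50% increase in peripheral blasts (WBC x % blasts") to above 25 x 10^9/L; and "New extramedullary disease".
- **Best overall response (12.1.4.3).** The window closes at progression or recurrence, and the reference for progression is the smallest value since treatment started.
- **Duration of overall response (12.1.5).** It ends at recurrent or progressive disease, taking as reference "the smallest measurements recorded since the treatment started". Stable disease duration also uses the smallest value.
- **Duration of CR (12.1.5).** "The duration of overall CR is measured from the time measurement criteria are first met for CR until the first date that progressive disease" has been documented. Recurrence is not mentioned and no reference value is given.
- **PFS (12.1.6).** "Progression-free survival (PFS) will be assessed, defined as the duration of time from start of treatment to time of progression or death", whichever is first. Again there is no mention of relapse or of a reference value.

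Section 12 contains no definition of relapse or recurrence.

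**The concern.** In acute leukemia, the event that normally ends a remission is relapse: blasts return after having been cleared. Here CR duration and PFS end on progression, and the leading marrow criterion for progression compares the patient with the disease burden before treatment. Someone whose blasts fall from 40% to 3% and return to 30% has plainly lost the remission, yet is still below the starting level. Under 12.1.4.1 as written, that patient no longer meets a response category and does not meet progression by marrow increase. Unless another progression route applies, the literal classification is stable disease.

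If the analysis follows the text, such patients either stay event-free or are censored when follow-up stops (Section 6.6: one month after removal from study). Both push the estimated curves upward. The conflict over the reference value adds a second problem: two analysts working from the same document could assign different progression dates to the same patient.

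**Working it through.** **Inputs.** CR requires marrow blasts below 5% and no circulating blasts (12.1.4.1). The marrow progression rule is as quoted above. Previously untreated patients qualify with at least 20% blasts in blood or marrow; relapsed or refractory patients may enter with any detectable burden; extramedullary disease qualifies in either setting (12.1.2). The plan states no event count, median or power for PFS or CR duration, so there is no figure of its own to reproduce on this point.

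**Step 1: marrow threshold with the baseline reference.** For baseline b (in %), progression needs blasts above 1.5 x b and, if b < 30, also at least b + 15. Below 30% the 15-point minimum is the binding part, because 0.5 x b < 15.

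| Baseline | Marrow blasts needed |
|---|---|
| 5% | 20% |
| 10% | 25% |
| 20% | 35% |
| 30% | >45% |
| 40% | >60% |
| 50% | >75% |
| 60% | >90% |
| 67% | >100.5%, unattainable |

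A patient with a baseline of 40% can lose CR anywhere from 5% to 60% marrow blasts without a marrow-increase event.

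**Step 2: do the other routes close the gap?** Only in part. The route above 70% needs at least 3 months' persistence, while follow-up ends one month after removal. The blood route needs more than 25 x 10^9/L, so circulating blasts that reappear below that level do not count. New extramedullary disease counts, but does not capture a relapse confined to marrow.

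**Step 3: the same patient with the smallest-value reference.** Take a baseline of 40% and a lowest value of 4%. By baseline, progression needs more than 1.5 x 40 = 60%. By lowest value, it needs more than 1.5 x 4 = 6%, or 4 + 15 = 19% if the 15-point minimum carries over. The text ties that minimum to baseline, so whether it carries over is unclear. From a lowest value of 0%, a percentage increase is undefined.

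**Step 4: how often would this matter?** The documents give no distribution of blasts at baseline or at relapse. Purely as an illustration with flat distributions, the share of baseline and relapse combinations meeting the marrow-increase criterion is:

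| Assumed baseline | Assumed relapse level | Baseline reference | Lowest value 4% + 15 points |
|---|---|---|---|
| 20-90% | 5-100% | 24% | 85% |
| 20-90% | 5-50% | 4% | 70% |
| 2-30% | 5-100% | 73% | 85% |
| 2-30% | 5-50% | 43% | 70% |

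The answer swings widely with the assumptions.

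**Step 5: the primary design.** Section 9.1 continues with at least 4 responses in 19 and declares success with at least 11 in 36. The probability of success is the sum over x = 4 to 19 of P(X1 = x) x P(X2 >= 11 - x), with X1 ~ Bin(19, p) and X2 ~ Bin(17, p). This gives 0.086 at p = 0.20 and 0.902 at p = 0.40, within the stated error limits of 0.10. Response at any time point is what counts, so a later relapse does not enter.

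**The case against.** A reader might infer that progression is measured only against baseline, so that relapse after CR will usually go uncounted. The documents do not support either part. Sections 12.1.4.3 and 12.1.5 use the smallest value for three other measures, and three of the progression routes are not written as a rise over baseline marrow blasts. How often relapse would be missed depends on blast levels that the documents do not give; low-burden relapsed or refractory patients may well meet the baseline rule.

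Nor does the problem extend in the same way to duration of overall response, which already ends at recurrence with the smallest-value reference. Its defect is narrower: the term is undefined.

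Two further points are fair. Section 12.1 says response and progression follow the 2017 European guideline, which may supply a relapse criterion; that cannot be checked from these documents. Even if it does, CR duration and PFS as worded do not call on it. And neither endpoint is a listed objective or a Section 9 endpoint. Section 9.4 plans Kaplan-Meier estimates by stratum without naming the outcome, so no go/no-go decision rests on them.

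These points limit the scope and consequence. They do not remove the gap in CR duration and PFS, or the conflict between the two references.

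**Conclusion.** The point holds in limited form. Read literally, CR duration and PFS do not count loss of remission until a progression criterion (or, for PFS, death) is met, and for moderate or high baseline blast counts the marrow-increase criterion sits far above the 5% that marks loss of CR. Both measures would be biased upward for some responders. The size cannot be computed; the thresholds above show where relapse can be missed, not how many patients will be affected. Section 12 also contradicts itself on the reference for progression and leaves recurrence undefined.

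This rests on the protocol's own wording being applied without an imported relapse definition. A reader might take it further, as a threat to the trial's efficacy conclusion; it is not, because the primary response rate and its two-stage rule do not depend on what happens after a response. It is still worth correcting, since Section 12.1.6 commits to assessing PFS.

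**What to change.** Make these changes in Section 12, stated to apply to endpoint analysis only:

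1. Define relapse after CR, CRi or MLFS. One option is the first date on which the marrow-blast, circulating-blast or extramedullary condition that the patient's remission category required in 12.1.4.1 is no longer met.
2. Name relapse, so defined, as an event for CR duration and PFS.
3. Apply the same definition to the word recurrent in duration of overall response.
4. Reconcile the baseline reference in 12.1.4.1 with the smallest-value reference in 12.1.4.3 and 12.1.5. If the smallest value is used for an endpoint, say whether the 15-point minimum carries over and how a lowest value of 0% is handled.

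Progression also takes patients off study (Sections 6.5 and 9.1). The text should therefore say that these analysis definitions leave the treatment-discontinuation rules unchanged.

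The cost is wording. Section 11 already schedules marrow examinations and blood counts, so no new assessment is needed. The downside is that reported PFS and CR duration will be somewhat shorter.
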